18. STATISTICAL CONSIDERATIONS

- **Analysis Population**

- **Safety Population**

The safety population will consist of all subjects who receive any amount of study treatment.

- **Safety Analysis**

Safety will be assessed by evaluation of AEs. All safety analyses will be performed using the safety population.

- **Adverse Events**

Adverse event terms recorded on the CRFs will be mapped to preferred terms using the Medical Dictionary for Regulatory Activities (MedDRA). Seriousness, severity grade and relationship to study treatment will be assessed by the investigator. Severity grade will be defined by the National Cancer Institute (NCI) CTCAE v4.0. Listings of AEs will be provided.

- **Sample Size**

The sample size will be up to 34 evaluable subjects in which the first 6 patients will be in the safety run-in phase with an interim futility assessment after 20 patients were treated.

(Evaluable subjects based on the primary endpoint are defined as subjects who received therapy on study and had at least one follow up scan after initiation of study treatment)

The ORR for this patient population is reported as 18% with pembrolizumab as a single agent. We estimate that the ORR will improve to about 35% with the combined treatment. We expect to accrue patients for 2 years and follow up for additional 12 months. The sample size will be 34 by a one-arm design with null hypothesis as ORR ≤ 0.15 vs. its one-sided alternative. If the number of responses is ≤ 9 out of 34, the trial will be claimed as not promising. The design yields a type 1 error of 0.05 and a power of 80% when the true response rate is 35%. An interim look after 20 patients will take place, and if ≤ 4 responses are observed, the trial will stop earlier and claim a futility.

Statistical analysis for biomarker studies: The ORR will be calculated with 95% confidence interval by Binomial distribution. The median PFS will be estimated by Kaplan-Meier method along with 95% confidence interval. The ability of biomarkers to predict ORR will be estimated by Chi-square test and/or logistic regression model, and association with PFS will be assessed by the Kaplan Meier method, Log-rank test, and Cox model, and the frequency of adverse events and serious adverse events will be summarized accordingly. The performance of predictability of biomarker for clinical outcomes will be described by AUC for binary outcome ORR and Uno's C-statistics for PFS with 95% CI and ranked accordingly.

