A run in phase of cabozantinib at 40 mg/day will be performed for the first 6 patients, beginning in Cycle 1. If the combination is well tolerated the trial will complete accrual at this dose level. If the combination is not well tolerated, with 2 DLTs observed in the first 6 patients, the dose of cabozantinib will be decreased to 20 mg/day which will be the dose used for the rest of the study.

Phase II:

Pembrolizumab will be administered at the standard dose of 200 mg Q 3 weeks. Cabozantinib will be given at the dose determined in the run in phase. Both agents will be initiated on Day 1 of Cycle 1 and will continue in combination.

NUMBER OF SUBJECTS

The sample size will be up to 34 subjects in which the first 6-9 patients will be in the safety run-in phase with an interim futility assessment after 20 patients were treated.

TARGET POPULATION

Cancer patients will be eligible for enrollment as defined by the inclusion and exclusion criteria as follows:

Inclusion Criteria

1. The subject has a histologic or cytologic diagnosis of squamous cell carcinoma of the oral cavity, oropharynx, paranasal sinuses, hypopharynx, nasopharynx or larynx. Squamous cell carcinoma of unknown primary in cervical lymph node can be included only if HPV status is positive.
2. Patients must have refractory, recurrent or metastatic disease, which is deemed to be inoperable.
3. In case patients received prior systemic therapy within the definitive or metastatic setting, disease progression must be documented following prior therapy; this can be in the recurrent or metastatic setting or in the concurrent setting.
4. Measurable disease per RECIST 1.1 as determined by the investigator;
5. A maximum of one prior radiotherapy regimen, curative or palliative, to the head and neck is allowed. If the radiation is combined with chemotherapy, a minimum of 4 months must elapse between the end of radiotherapy and registration. If the radiation is given alone, a minimum of 8 weeks must elapse between the end of radiotherapy and registration. A minimum of 3 weeks must elapse between prior radiation to other areas and registration. Treatment areas should be healed with no sequelae from RT that would predispose to fistula formation
6. The subject has had an assessment of all known disease sites eg, by computerized tomography (CT) scan, magnetic resonance imaging (MRI), bone scan or PET/CT scan as appropriate, within 28 days before the first dose of cabozantinib;

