- Tumor DNA whole exome sequencing and RNA sequencing to determine potential neoantigens and their expression.

Blood samples will be collected at screening, at 9 weeks on treatment, at 6 months on treatment, and end of treatment (or disease progression whichever is sooner).

- Plasma biomarkers will include HGF, IL-6, IL-8, VEGF, and IFN- γ determined by ELISA analyses.
- Circulating cell free DNA (cfDNA) in plasma will be determined by DNA sequencing.
- Peripheral blood mononuclear cells (PBMC) will be evaluated by flow cytometry for immune monitoring.

For a quantitative radiomics, CT and/or PET images will also be collected. For quantitative pathomics, digitized H&E images will also be collected.

STATISTICAL METHODS

The sample size will be up to 34 subjects in which the first 6 patients will be in the safety run-in phase with an interim futility assessment after 20 patients were treated.

The ORR for this patient population is reported as 18% with pembrolizumab as a single agent. We estimate that the ORR will improve to about 35% with the combined treatment. We expect to accrue patients for 2 years and follow up for additional 12 months. The sample size will be 34 by a one-arm design with null hypothesis as ORR ≤ 0.15 vs. its one-sided alternative. If the number of responses is ≤ 9 out of 34, the trial will be claimed as not promising. The design yields a type 1 error of 0.05 and a power of 80% when the true response rate is 35%. An interim look after 20 patients will take place, and if ≤ 4 responses are observed, the trial will stop earlier and claim a futility.

Statistical analysis for biomarker studies: The ORR will be calculated with 95% confidence interval by Binomial distribution. The median PFS will be estimated by Kaplan-Meier method along with 95% confidence interval. The ability of biomarkers to predict ORR will be estimated by Chi-square test and/or logistic regression model, and association with PFS will be assessed by the Kaplan Meier method, Log-rank test, and Cox model, and the frequency of adverse events and serious adverse events will be summarized accordingly.

TABLE OF CONTENTS

TABLE OF CONTENTS.....	10
1 BACKGROUND AND RATIONALE.....	16
1.1 Background:	16
1.2 Cabozantinib (XL184)	22
1.2.1 Pharmacology	22
1.2.2 Cabozantinib Nonclinical Toxicology	24
1.2.3 Clinical Experience	24
1.2.3.1 Clinical Summary	24
1.2.3.2 Clinical Safety Profile.....	24
1.2.3.3 Clinical Pharmacokinetics	26
1.2.3.4 Clinical Activity.....	26

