2 STUDY OBJECTIVES AND DESIGN

2.1 Study Objectives

The objectives of this study are as follows:

Primary Objectives:

To estimate the overall response rate (ORR) of patients with RM SCCHN who receive the combination of pembrolizumab and cabozantinib.

Secondary Objectives:

- To estimate the progression-free survival (PFS) of patients treated with the combination of pembrolizumab and cabozantinib.
- To further define the toxicities associated with these regimens in patients with SCCHN.

Exploratory Objectives:

- To identify potential biomarkers related to response to the combination of pembrolizumab and cabozantinib in patients with RM SCCHN. Specifically, to evaluate whether markers of angiogenesis, hypoxia, Met or pMet expression, or inflammatory activation can predict response to the combination or PFS.
- To gather exploratory clinical data on a potentially predictive set of biomarkers (potential biomarkers include MET expression by FISH, NGS and IHC/IHF of cMET, pMET, HGF, HER2, HER3 and heregulin mRNA level).
- To evaluate circulating cell free DNA (cfDNA) in plasma and its association with response to the combination or PFS.
- To evaluate potential neoantigens in the tumor DNA, their expression, and their association with response to the combination or PFS.
- Evaluate peripheral blood mononuclear cells (PBMC) for immune monitoring and their association with response to the combination or PFS.
- To determine a quantitative radiomics based on CT and/or PET images as a prognostic biomarker in recurrent or metastatic HNSCC.
 - To determine a computational pathology (or pathomics) based prognostic marker from standard digitized H&E images of the tumor in recurrent or metastatic HNSCC.
-

Endpoints

Primary Endpoint

ORR: The proportion of subjects with partial response (PR) or complete response

(CR) as defined by RECIST v1.1 response criteria.

Secondary Endpoints

PFS: The duration from date of treatment start to the date of objectively documented progression or death due to any cause, whichever status is recorded first.

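### Section 18 counts 34 scanned subjects while the endpoint and synopsis say only subjects; on the natural reading, treated patients never scanned drop out of the response rate and bias it upward.

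*Combined protocol and SAP*

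**What the plan says.** Three bases for counting patients appear.

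- **Evaluable.** The Sample Size part of Section 18 opens with "The sample size will be up to 34 evaluable subjects in which the first 6 patients will be in the safety run-in phase" and then gives the definition: "Evaluable subjects based on the primary endpoint are defined as subjects who received therapy on study and had at least one follow up scan" after starting treatment.
- **Treated.** The same opening sentence places the interim by a different count: "with an interim futility assessment after 20 patients were treated". The only analysis population with its own heading in Section 18 is also based on treatment: "The safety population will consist of all subjects who receive any amount of study treatment".
- **Subjects, unqualified.** Section 2.1 defines ORR as "The proportion of subjects with partial response (PR) or complete response" by RECIST 1.1. The synopsis has "The sample size will be up to 34 subjects in which the first 6-9 patients will be in the safety run-in phase" under Number of Subjects and "The sample size will be up to 34 subjects in which the first 6 patients will be in the safety run-in phase" under Statistical Methods, both without the scan condition.

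The decision rule in Section 18 (9 or fewer out of 34 is not promising) carries no qualifier, and the analysis sentence names no denominator: "The ORR will be calculated with 95% confidence interval by Binomial distribution".

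Two other places come near the question. The text beside Table 3-2 in Section 3.3 covers patients removed after more than six weeks off both drugs: response is assessed if available, and intent to treat is named with OS and PFS. Section 3.4.4 says that patients given palliative radiation to bone may be treated as not evaluable for some efficacy endpoints. Neither says whether a treated, unscanned patient is a non-responder, is excluded or is replaced.

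On-treatment scans are every nine weeks from the first day of cycle 1 (Table 16-1, footnote i); Section 16 allows earlier assessments when clinically indicated.

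**The concern.** A patient who dies, deteriorates or stops treatment before week 9 may have no follow-up scan. Such a patient cannot be a RECIST responder, so leaving the patient out of the denominator can only raise the ORR. The trial has one arm and is judged against a fixed 15%, so no comparator carries the same bias to offset it. At stake are the size of the reported ORR, the meaning of the 10-of-34 success threshold, and the risk that the denominator is chosen after the data are seen.

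**Working it through.** **Inputs.** From Section 18: null ORR 15%, alternative 35%, stop if 4 or fewer responses at 20, promising if 10 or more of 34, stated error 0.05 and power 80%. Assumed, because the documents do not give it: f, the share of treated patients never scanned, taken as 5%, 10%, 15% and 20%.

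**Step 1: the plan's own figures.** Ignoring the interim, P(X ≥ 10 | 34, 0.15) = 0.024 and P(X ≥ 10 | 34, 0.35) = 0.804, so the stated 80% is reproduced and the error lies inside 0.05. With the interim, the sum over x ≥ 5 of Bin(x; 20, p) × P(Bin(14, p) ≥ 10 − x) gives 0.021 at 15% and 0.771 at 35%.

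**Step 2: inflation of the estimate.** Let p be the ORR among all treated. Unscanned patients contribute no responses, so the ORR among scanned patients is q = p/(1 − f). Reaching 34 evaluable takes about 34/(1 − f) treated.

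| f | 0.15/(1 − f) | Treated for 34 evaluable |
|---|---|---|
| 5% | 15.8% | 35.8 |
| 10% | 16.7% | 37.8 |
| 15% | 17.6% | 40.0 |
| 20% | 18.8% | 42.5 |

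**Step 3: false-promising rate at a true all-treated 15%, accrual to 34 evaluable.**

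(a) Interim on 20 treated, as written. Let m ~ Bin(20, 1 − f) be the number scanned among those 20. Sum over m and x ≥ 5: P(m) × Bin(x; m, q) × P(Bin(34 − m, q) ≥ 10 − x).

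(b) Both looks on evaluable subjects. Use the Step 1 two-stage formula with q in place of p.

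| f | (a) interim on treated | (b) both on evaluable |
|---|---|---|
| 0 | 2.1% | 2.1% |
| 5% | 2.8% | 2.9% |
| 10% | 3.6% | 4.1% |
| 15% | 4.5% | 5.7% |
| 20% | 5.7% | 8.0% |

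The 0.05 line is crossed at f of about 17% in (a) and about 13% in (b).

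(c) Only 34 treated, 10 responses still required. Dropping unscanned patients changes the reported percentage but not the number of responses, so the rate stays at 2.1% for every f.

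**Step 4: power under an all-treated rule** (34 treated, unscanned counted as non-responders, interim kept). If 35% is the all-treated rate, power is 77.1% for every f. If 35% is the rate among evaluable patients, the all-treated rate is 0.35 × (1 − f). The as-written column is formula (a) with q = 0.35.

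| f | All-treated ORR | Power, all-treated rule | Power, as written |
|---|---|---|---|
| 5% | 33.3% | 70.5% | 75.0% |
| 10% | 31.5% | 62.9% | 72.1% |
| 15% | 29.8% | 54.5% | 68.4% |

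**The case against.** The strongest reply has four parts.

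1. *The denominator is close to stated.* Evaluability is defined for the primary endpoint, beside the figure of 34 and ahead of the decision rule. If that is the denominator, the result can be reproduced, and the synopsis is merely abbreviating. This stands in part. A reader might infer that the ORR cannot be reproduced on any reading; the documents do not support that, because the evaluable reading yields a definite number. But that reading is also the one that biases the estimate, and neither the endpoint definition nor the analysis sentence adopts it.

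2. *Nothing states that unscanned patients are excluded or that accrual passes 34 treated.* The synopsis caps the trial at 34 subjects, and the only replacement rule (Section 2.2.1) concerns DLT evaluability. This stands as a limit: exclusion is an inference, and under case (c) the error does not rise. Against it, a target of 34 evaluable subjects implies treating more than 34 if any go unscanned.

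3. *Few patients should be lost before week 9.* Section 4.1 requires life expectancy above three months and ECOG 0 or 1, and unscheduled scans are allowed. This makes a small f more plausible but does not make it zero. Early deaths also count in PFS, which does not correct the ORR.

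4. *The error effect is small.* This stands. A reader might infer that the trial exceeds its 5% error. With the interim on 20 treated, that needs f above about 17%, and the documents give no f.

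**Conclusion.** The concern holds as a bias in the primary estimate and an unsettled denominator, not as a demonstrated breach of type I error. On the natural reading, the reported ORR is the all-treated ORR divided by (1 − f), so a true 15% reads as 15.8% to 18.8% for f from 5% to 20%. The false-promising rate rises from 2.1% to between 2.8% and 5.7% with the interim on treated patients; slack in the 10-of-34 rule absorbs the effect until f is about 17%, or about 13% if both looks use evaluable subjects.

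This rests on three things: the inference that the 34 in the decision rule are evaluable subjects, accrual continuing to 34 of them (for the error figures only), and an assumed f. The gap in the text is certain; the size of the bias is not known. It should be fixed, because following the definition in Section 18 gives a worse estimate than an available alternative that needs only wording.

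**What to change.** In Section 18, define the primary ORR population as all patients who receive any study treatment, count those with no post-baseline scan as non-responders, and keep the evaluable set as a sensitivity analysis. Use that one basis for the interim 20 and the final 34 in Section 18 and in both synopsis statements, and name the same denominator in the endpoint definition in Section 2.1. Leave the decision rule as it is. State whether 35% is a rate among all treated or among evaluable patients.

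The cost is wording and a slightly lower reported ORR. If 35% is an all-treated rate, the existing rule has error 2.1% and power 77.1% with the interim, whatever f is. If it is an evaluable rate, power with 34 treated falls to 70.5%, 62.9% and 54.5% at f of 5%, 10% and 15%, against 75.0%, 72.1% and 68.4% as written. In either case the stated 80% should be restated to match.

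### The stated 80% power ignores the interim futility stop: with the ≤4/20 stop and the ≤9/34 cut-off, exact power at a true ORR of 35% is 77.1%

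*Combined protocol and SAP*

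**What the plan says.** The Sample Size text of Section 18 sets out one design, and the Statistical Methods part of the synopsis gives the same null, final rule, interim rule and error rates.

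- Null and size: "The sample size will be 34 by a one-arm design with null hypothesis as ORR ≤ 0.15 vs. its one-sided alternative".
- Final rule: "If the number of responses is ≤ 9 out of 34, the trial will be claimed as not promising". A positive result therefore needs at least 10 responses.
- Stated properties: "The design yields a type 1 error of 0.05 and a power of 80% when the true response rate is 35" (per cent).
- Interim rule, in the next sentence: "An interim look after 20 patients will take place, and if ≤ 4 responses are observed, the trial will stop earlier and claim a futility". Continuing therefore needs at least 5 responses in 20.
- Denominators: the total is given as "The sample size will be up to 34 evaluable subjects", while the look is described as "an interim futility assessment after 20 patients were treated". Section 18 defines evaluable as having received therapy and had at least one follow-up scan.

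Neither place says that the 80% excludes the interim look, or that the stop is advisory.

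**The concern.** A futility stop can only lower power, because some trials halted at the look would have recovered and met the final rule. Here the power sentence comes before the interim rule and is not revisited, so it is unclear whether the 80% allows for the stop. The stop is not a lenient one: 4 of 20 is an observed rate of 20%, above the 15% null and above the 18% quoted for pembrolizumab alone.

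If the 80% leaves the stop out, the protocol overstates its ability to detect the effect it was sized for. This matters most when the trial is negative or stops early, because a reader then uses the stated power to judge how firmly a 35% response rate has been ruled out.

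**Working it through.** **Inputs (Section 18, Sample Size).** Null ORR 0.15, one-sided; alternative 0.35; N = 34; not promising at ≤9/34; stop at ≤4/20.

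**Step 1. Reproduce the stated figure without the interim.** With X ~ Bin(34, p), success is X ≥ 10.

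- p = 0.35: P(X ≥ 10) = 0.8045, which matches the stated 80%.
- p = 0.15: P(X ≥ 10) = 0.0240.
- Next lower cut-off (≤8/34) at p = 0.15: P(X ≥ 9) = 0.0587, above 0.05. So ≤9 is the smallest single-stage cut-off that keeps type 1 error within 0.05.

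A normal approximation at N = 34 does not explain the 80%: it gives 88.8% at one-sided 0.05 and 83.6% at one-sided 0.025.

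**Step 2. Add the stop.** Let X1 ~ Bin(20, p) be responses at the look and X2 ~ Bin(14, p) those in the remaining 14. Success needs X1 ≥ 5 and X1 + X2 ≥ 10:

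Power = Σ (x = 5 to 20) P(X1 = x) × P(X2 ≥ 10 − x)

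At p = 0.35:

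| X1 | P(X1) | P(X2 ≥ 10 − X1) | Product |
|---|---|---|---|
| 5 | 0.1272 | 0.5773 | 0.0734 |
| 6 | 0.1712 | 0.7795 | 0.1335 |
| 7 | 0.1844 | 0.9161 | 0.1689 |
| 8 | 0.1614 | 0.9795 | 0.1580 |
| 9 | 0.1158 | 0.9976 | 0.1156 |
| ≥10 | 0.1218 | 1 | 0.1218 |
| **Sum** | | | **0.7712** |

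A simulation of 4 million trials gave 0.7713. The same sum at p = 0.15 gives a type 1 error of 0.0213.

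**Step 3. Size of the loss.**

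- Against the single-stage rule: 0.8045 − 0.7712 = 0.0333, or 3.3 points.
- Against the stated figure: 80 − 77.1 = 2.9 points.
- Risk of missing a true 35%: 1 − 0.7712 = 0.2288. The interim accounts for 0.0333 / 0.2288 = 14.5% of it.
- Probability of stopping at the look: P(X1 ≤ 4) = 0.1182 at 35% and 0.8298 at 15%.
- Of the stops at a true 35%, 0.0333 / 0.1182 = 28% would have gone on to at least 10/34.
- Power with the stop reaches 80% at a true ORR of 35.9%.

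**Step 4. Sensitivity to the interim denominator.** If some of the 20 treated patients are not evaluable and the ≤4 rule is unchanged, power falls further. The documents give no rate of non-evaluability, so these counts are assumptions: with 19 of the 20 evaluable, power is 75.3%; with 18, it is 72.8%.

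**The case against.** Four points can be made for the plan.

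1. *The 80% describes the final rule only.* The power sentence directly follows the 34-subject, ≤9/34 rule, and for that rule it is correct. On this view the statement is incomplete rather than wrong. However, the opening sentence of the same section already makes the futility assessment part of the design, so a reader will reasonably take the design's power to include it.

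2. *The cut-off itself may be misprinted.* With the ≤4/20 stop kept and a final cut-off of ≤8/34, type 1 error is 0.047 and power 83.5%. Both stated figures then hold as limits with the interim included. This fits 80% less closely than the single-stage 80.4%, but it cannot be excluded from the documents. This point stands: the cut-off should be confirmed before new figures are written in. It does not rescue the current text, since the decision rule would then be the part in error.

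3. *The stop might be applied with discretion.* Power would then lie between 77.1% and 80.4%. The wording gives no such latitude.

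4. *The effect is small.* This is true. The gap is under 3 points, the planning value is itself described as approximate, the primary objective is estimation of ORR with a confidence interval, and false-positive control at 15% is not weakened. These facts limit the importance of the point but do not make the stated power correct.

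**Conclusion.** The point holds. Under the rules as written, power at a true ORR of 35% is 77.1%, not 80%, and type 1 error at 15% is 0.021. With the stated ≤9/34 cut-off, the 80% is recovered only by leaving out the ≤4/20 stop, which makes that omission the likeliest cause.

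The result rests on two assumptions: the stop is binding, as its wording indicates, and the 20 are the first 20 of the 34 evaluable subjects, with their responses known at the look. If fewer than 20 are evaluable at the look, the shortfall is larger. The consequence is a modest overstatement of sensitivity in two places. It should be corrected, but it does not undermine the design.

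**What to change.** First confirm that ≤9/34 is the intended final cut-off. If it is, keep the rules and replace the properties sentence in both the synopsis and Section 18 with wording such as: *exact type 1 error 0.021 (nominal limit 0.05) at an ORR of 15% and power 77% at an ORR of 35%, including the interim look; the futility stop is binding and is assessed on the first 20 evaluable subjects.*

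Restating the figures costs only wording: the thresholds and the 34 subjects are unchanged, and the quoted power becomes slightly less favourable. Defining the 20 as evaluable goes a little further, because the look must then wait for a follow-up scan on the 20th evaluable subject. If the look stays on treated patients, say that 77% assumes all 20 are evaluable.

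If the sponsor would rather recover the power, there are two options with N = 34. Both are design choices and neither is needed for the correction.

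- Stop at ≤3/20 and keep ≤9/34: type 1 error 0.023 and power 79.8%, but the chance of stopping early at a true 15% falls from 83% to 65%.
- Keep ≤4/20 and use ≤8/34: type 1 error 0.047 and power 83.5%, but the chance of a promising claim at the 18% single-agent rate is 11.8%.

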19. OTHER ANALYSES

Tumor samples will be collected from all patients through archival tissue or biopsies performed from at least one site of disease prior to the first dose administration of therapy. Tumor samples collected through these biopsies will be compared with the historical samples and will also be analyzed to explore the biomarkers that could predict response to cabozantinib. Optional end of treatment tumor biopsy (or at the time of progression) is allowed at both Emory Winship Cancer Institute and Moffitt Cancer Center.

Baseline biopsies or surgical specimens from trial participants will be analyzed for the following:

- Tumor pVEGFR2/VEGFR2, pMet/Met, pSTAT3/STAT3, and PD-L1 protein expression as well as markers of hypoxia, antigen presenting cells, T cells, and B cells among the Tumor infiltrating immune cells using multiplex immunohistochemistry (IHC).
- Tumor DNA whole exome sequencing and RNA sequencing to determine potential neoantigens and their expression.

Blood samples will be collected at screening, at 9 weeks on treatment, at 6 months on treatment, and end of treatment (or disease progression whichever is sooner).

- Plasma biomarkers will include HGF, IL-6, IL-8, VEGF, and IFN- γ determined by ELISA analyses.
- Circulating cell free DNA (cfDNA) in plasma will be determined by DNA sequencing.
- Peripheral blood mononuclear cells (PBMC) will be evaluated by flow cytometry for immune monitoring.

For detailed tissue collection and processing information, please see **LAB MANUAL**.

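### Exploratory biomarkers are ranked by AUC and Uno's C in at most 34 patients with no stated internal validation or selection adjustment, so the top-ranked estimate is biased upward

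*Combined protocol and SAP*

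**What the plan says.** The Sample Size part of section 18 (Statistical Considerations) sets out the biomarker analysis in one paragraph. For response, "The ability of biomarkers to predict ORR will be estimated by Chi-square test and/or logistic regression model". For PFS it names Kaplan-Meier, log-rank and Cox methods. It then adds that performance will be "described by AUC for binary outcome ORR and Uno's C-statistics for PFS with 95% CI and ranked accordingly". The same section gives the size of the data set: "The sample size will be up to 34 evaluable subjects".

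The candidates are spread over two places.
- Section 19 (Other Analyses) lists multiplex IHC markers, exome and RNA sequencing for neoantigens, cell-free DNA and PBMC flow cytometry. For the ELISA panel it says "Plasma biomarkers will include HGF, IL-6, IL-8, VEGF, and IFN"-γ.
- Section 2.1 (Study Objectives) adds MET by FISH and NGS, HGF, HER2, HER3 and heregulin, and two image-based aims. One reads "To determine a quantitative radiomics based on CT and/or PET images as a prognostic biomarker in recurrent or metastatic HNSCC"; the other is the pathology-image equivalent.

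All of these are exploratory objectives, and section 2.1 calls the markers potential. The documents give no number of candidates, lead marker, preset direction, cross-validation, bootstrap, permutation reference, validation set or multiplicity rule for them. The only multiplicity remark, in section 1.2.3.4, concerns an earlier cabozantinib trial.

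**The concern.** Ranking picks the largest of many estimates, each with a large standard error at this sample size. The largest is too high on average even when every individual estimate is unbiased. A 95% CI computed as though that marker had been the only one examined does not have 95% coverage for it.

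No decision within the trial depends on the ranking. What is at stake is the product of the exploratory objective: an ordered list whose leading entry may be taken forward because its AUC looks respectable and its interval clears 0.5. The exploratory label tells the reader to be cautious, but it does not correct the number.

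**Working it through.** **Stated figures.** The documents give no figure for the biomarker analysis. The design figures it rests on are p0 = 0.15, p1 = 0.35, N = 34, and not promising at 9 or fewer responses. As a fixed-sample exact binomial, P(X ≥ 10 | 34, 0.35) = 0.8045, so the stated N and 80% power reproduce (P(X ≥ 10 | 34, 0.15) = 0.0240).

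**Responders.** From "We estimate that the ORR will improve to about 35% with the combined treatment": 0.35 × 34 = 11.9, so 12 responders and 22 non-responders.

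**Candidates (assumption, shown as a range).**
- Low count: section 19 names 8 IHC markers or groups (VEGFR2, Met and STAT3 each paired with the phosphorylated form; PD-L1; hypoxia; antigen-presenting cells; T cells; B cells) and 5 plasma proteins. 8 + 5 = 13.
- High count: splitting the three pairs gives 11 IHC markers. With 5 plasma proteins, cell-free DNA, PBMC and neoantigens that is 19. Section 2.1 adds MET by FISH/NGS, HGF, HER2, HER3, heregulin, radiomics and pathomics, 7 more, so about 26. Counting individual imaging or sequencing features would give more.

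**Precision of one AUC.** The Hanley-McNeil variance is [A(1−A) + (n1−1)(Q1−A²) + (n0−1)(Q2−A²)]/(n1·n0), with Q1 = A/(2−A) and Q2 = 2A²/(1+A).
- At A = 0.5, n1 = 12, n0 = 22: (0.25 + 11 × 0.0833 + 21 × 0.0833)/264 = 0.01105, SE 0.105, 95% half-width 0.206.
- At A = 0.70: (0.21 + 11 × 0.0485 + 21 × 0.0865)/264 = 0.00969, SE 0.098, lower limit 0.70 − 1.96 × 0.098 = 0.507.

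So an observed AUC of about 0.70 is enough for the interval to exclude 0.5.

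**Simulation with no predictive marker.** Continuous noise markers, 34 patients, 12 responders, ordinary 95% CI. Ranges run from pairwise correlation 0.5 to independence.

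| Markers | Mean best AUC, direction from data | CI excludes 0.5, direction from data | CI excludes 0.5, all directions preset |
|---|---|---|---|
| 1 (named in advance) | – | 6% | – |
| 13 | 0.69-0.71 | 44-57% | 21-35% |
| 26 | 0.71-0.73 | 59-82% | 32-57% |

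DeLong and Hanley-McNeil intervals and repeated runs differ by a few percentage points.

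**Scale.** With independent markers and direction chosen from the data, the best AUC would have to exceed about 0.79 (10 markers), 0.80 (16), 0.81 (20) or 0.83 (50) to beat chance at 5% familywise. For one pre-named marker the figure is 0.705.

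**Fewer responders** (16 independent markers). With 6 responders of 34, the mean best AUC is 0.77 and the CI excludes 0.5 in 73%. If the trial stops at the interim with 4 of 20, the figures are 0.83 and 83%.

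**Uno's C for PFS.** With 24 months' accrual plus 12 months' follow-up, truncation at 24 months and an assumed median PFS of 3 to 12 months, the mean best C is 0.61-0.62 (10 markers), 0.62-0.63 (16) and 0.65-0.66 (50).

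**Does correction help?** A bootstrap optimism correction with selection repeated in every resample brought mean best AUCs of 0.71 (13 markers) and 0.73 (26) down to about 0.57-0.58. The excess over 0.5 falls from 0.21-0.23 to 0.07-0.08, so about two-thirds of it is removed.

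**The case against.** The strongest reply is that this is a descriptive, exploratory analysis on which nothing in the trial turns. That stands as a limit on the importance of the point. It does not answer the bias, which comes from selecting the maximum whatever the analysis is called.

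Several stronger readings are tempting, and the documents do not support them.
- A reader might infer that section 18 prescribes uncorrected resubstitution AUCs with a plain CI. It prescribes neither; both are inferred from its silence. The defect is under-specification.
- A reader might infer that the plan names 26 markers. It gives no count, and 26 is one way of counting.
- A reader might infer that the top marker is bound to look predictive. The chance is about 21-82%, depending on marker number, correlation and preset direction. Correlation is plausible, since the list pairs phosphorylated with total protein. All these figures also suppose that no marker is truly predictive.
- A reader might infer that radiomic and pathomic signatures will be built and scored on the same patients. Section 2.1 states the aim without saying where training or testing takes place.
- A reader might want the 9-week and 6-month samples analysed only against PFS. Section 2.1 plans cell-free DNA and PBMC associations with response as well, and nothing in this point requires dropping them.

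The simulation treats markers as continuous and complete in all 34 patients. The planned chi-square test implies that some will be categorised, and missing samples would change the figures.

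**Conclusion.** The point holds as a gap in specification with a predictable direction of bias. Section 18 ranks markers and attaches 95% CIs, and nothing in the documents corrects for the ranking, so the leading AUC will on average be too high and its interval too favourable. With 12 responders and no predictive marker, the best AUC sits near 0.7. Its CI excludes 0.5 several times as often as the 6% seen for a single pre-named marker, even when all directions are preset. The problem grows if responders are fewer or individual imaging or sequencing features are ranked, and it is milder for Uno's C. The sizes rest on assumed counts of 13 to 26, correlation between 0 and 0.5, and complete continuous data. Because the objective is exploratory, this is a worthwhile improvement and does not threaten the trial's primary conclusion.

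**What to change.** Add to section 18:
1. A list of the candidate markers to be ranked, with any direction of effect fixed in advance.
2. Bootstrap optimism-corrected AUC and Uno's C beside the apparent values. Repeat marker selection, direction choice, cut-point search and any radiomic or pathomic signature building done on these patients inside each resample.
3. Rank-stability intervals from the same resamples, and false-discovery-rate-adjusted p-values beside the raw ones. The adjustment needs the list in item 1 to define its denominator.
4. A statement that the ranking is hypothesis-generating.

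This needs no extra patients, samples or visits. The cost is some analysis code and less favourable reported AUCs. The correction removes most of the optimism but not all of it, which is a further reason for item 4.
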